4.0 Preliminary Investigations and Justification

4.1 Literature Review and Justification

Please reference the Investigator's Brochure for a complete literature review and study justification.

4.2 Non-clinical Testing

Non-clinical tests were conducted in accordance with Good Laboratory Practice requirements or performed in compliance with verified methods and Standard Operating Procedures to maintain the integrity of the results. Please reference the Clinical Investigator's Brochure for a summary of non-clinical testing.

4.3 Previous Clinical Experience

Please reference the Investigator's Brochure for a complete description of previous clinical experience with AMDC.

5.0 Risk Analysis and Risk Assessment

5.1 Risks and Foreseeable Adverse Product Effects

Please reference the Investigator's Brochure for a summary of the complete risk analysis.

5.2 Methods to Minimize Risks

The procedure for proper deployment of the product at the intended site is described in the Summary Description of Procedures and the Instructions for Use (Sections 3.3.1 and 3.3.2). Only qualified physicians experienced in performing anorectal procedures will inject the product. Appropriate patient selection and adherence to and training on the research protocol are necessary to reduce product- and procedure-related risk. Routine venipuncture will be performed by qualified personnel.

Injection of AMDC will occur under direct vision. The presence of bleeding or puncture will be ascertained following injection. In addition, this investigation includes a high level of monitoring. The risks of continued incontinence, infection, and allergic reaction to the injected reagents will be assessed through patient report, a patient fecal incontinence diary that will be kept at various time points throughout the study, and clinical follow-up at 3, 6, and 12 months after treatment. Patients will be contacted by phone 24-48 hours and one month after injection to assess for adverse events.

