2.0 Objectives of the Clinical Investigation

2.1 Primary Objective

The primary objective is to determine the incidence of product- or procedure-related adverse events associated with the use of AMDC within 12 months post-treatment.

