6.7 Description of Methods at Patient Visits

The schedule of exams specific to study visits (time points) is provided in Table 6-1. A detailed study flow diagram is provided in Appendix A. Note that the time windows indicated for specific visits are suggested guidelines, not absolute requirements. The exams/tests specified at each visit (study time point) may be combined in any number of actual visits to accommodate site and patient scheduling as necessary.

Regarding study medications, there are no specific medication requirements for patients participating in this study. Patients are to be prescribed medications according to the standard of care at the respective investigative site. To the greatest degree possible, a patient's medication regimen related to fecal incontinence should be maintained constant during the entire course of the study. Patient medication usage will be captured in the medication log.

Table 6-1: Exam Visit Schedule

Study Time Point	Pre-enrollment Screening and Baseline ¹	Biopsy ¹	AMDC Injection Procedure	Post-treatment Follow-up ¹				
	Week -16 to -8			Day 0	Day 1 to 2	Month 1	Month 3	Month 6
	Visit 1	Visit 2	Visit 3		Phone	Phone	Visit 4	Visit 5
Informed Consent	X							
Patient History	X							
Medications Log	X	X	X	X	X	X	X	X
Blood-Borne Pathogens (HBV, HCV, Syphilis, HIV) ²		X						
Pregnancy Test ³	X	X	X					
Clinical Assessment ⁴	X		X			X	X	X
FIQL ⁵	X					X	X	X
Wexner Score	X					X	X	X
Patient Fecal Incontinence Diary ⁶		X	X			X	X	X
Endoanal Ultrasound	X ⁷							X
Anorectal Manometry	X ⁷							X
Muscle Biopsy		X						
AMDC Injection			X					
Phone Contact				X	X			
Adverse Events	X	X	X	X	X	X	X	X

¹ Exams/assessments may be completed at multiple actual visits as necessary to accommodate patient and hospital scheduling.

² If the biopsy procedure takes place more than 30 days after the blood-borne pathogens tests were completed during screening, the blood-borne pathogen tests (Hepatitis B, Hepatitis C, HIV, and syphilis) and risk assessment of HTLV-1 (and HTLV-1 antibody test if applicable) must be repeated before the biopsy procedure to confirm the patient's continued eligibility for study participation. Additionally, the blood-borne pathogens tests needs to be repeated at the time of donation or, if not possible, within seven days post donation.

³ Pregnancy test is not required if the patient has had a previous hysterectomy and/or is post-menopausal.

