6.7.2 Visit 2 (Week -8 to -6): Biopsy

After patient eligibility is confirmed, patients will return to the clinic for an outpatient procedure in which muscle tissue is obtained using a needle biopsy technique [REDACTED]. The blood-borne pathogens tests (Hepatitis B, Hepatitis C, syphilis, and HIV) and a risk assessment of HTLV-1 needs to be repeated at the time of donation or, if not possible, within seven days post donation. Note that several passes of the biopsy needle may be required to obtain a satisfactory sample of muscle tissue. Additionally, if the first biopsy does not produce

an adequate sample for product isolation, it may be necessary for the patient to return for another biopsy procedure. [REDACTED]

[REDACTED] If appropriate, patients will also have a urine sample collected for pregnancy testing, which would be repeated at any additional biopsy visits if more than one biopsy is required. The medication log will be updated if necessary and adverse events will be recorded and reported as appropriate. Additionally, patients will be given a 28-day diary to report fecal incontinence data and instructions on how to complete the diary. The diary should be started approximately 1 week after the biopsy procedure, completed during the subsequent 28 days, and returned to the site at the next scheduled visit (injection visit).

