6.7.4 Phone Contact (Day 1 to 2): Post-treatment Follow-up

Between 24 and 48 hours after treatment, patients will be contacted by phone to determine if any adverse events have occurred and if the patient has any updates for the medication log.

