6.7.5 Phone Contact (Month 1, ± 1 week): Post-treatment Follow-up

One month after the AMDC injection procedure the patients will be contacted by phone to determine if any adverse events have occurred and if the patients have any updates for the medication log.

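### No routine adverse event contact is described between the muscle biopsy and the injection visit, so short-lived biopsy events are liable to be under-recorded in the study's safety data

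*Combined protocol and SAP*

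**What the plan says.** The study has two invasive steps. The biopsy is described in section 3.3.1 as minor surgery with a skin incision of about 5 mm. Section 3.3.2 adds incision of the deep fascia. Section 6.7.2 warns that "several passes of the biopsy needle may be required to obtain a satisfactory sample of muscle tissue" and allows for a return visit for a second biopsy. Enrollment takes place at the biopsy (section 6.5).

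Two adverse event calls are planned, and both follow the injection. Section 5.2 says "Patients will be contacted by phone 24-48 hours and one month after injection to assess for adverse events". Section 6.7.4 says "Between 24 and 48 hours after treatment, patients will be contacted by phone to determine if any adverse events have occurred", and section 6.7.5 says "One month after the AMDC injection procedure the patients will be contacted by phone to determine if any adverse events have occurred". The Phone Contact row of Table 6-1 marks only these two.

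The Adverse Events row of Table 6-1 marks every time point, and sections 6.7.2 and 6.7.3 both have adverse events recorded at the biopsy and injection visits. In between, the patient keeps a fecal incontinence diary, to be "returned to the site at the next scheduled visit (injection visit").

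The interval comes from the heading "6.7.2 Visit 2 (Week -8 to -6): Biopsy". Section 6.7 qualifies all such intervals: "Note that the time windows indicated for specific visits are suggested guidelines, not absolute requirements". The interval stated in section 6.7.3 is redacted.

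The primary objective (section 2.1) is to "determine the incidence of product- or procedure-related adverse events associated with the use of AMDC", limited to 12 months post-treatment. Section 2.2 lists safety measured by adverse events as a secondary objective and gives no window. Section 6.10 requires all adverse events, related or not, to be reported within ten days of the site learning of them.

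**The concern.** The plan solicits adverse events promptly after one invasive step and not after the other. Bruising, pain, numbness or a minor wound infection that clears within a few weeks of the biopsy would first be asked about at Visit 3, when the patient may no longer remember it or think it worth mentioning. A patient who has the biopsy but never reaches injection has no Visit 3.

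This study exists mainly to describe safety. If the two procedures are ascertained with different intensity, their event rates are not comparable, and the biopsy will tend to look safer than it is.

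**Working it through.** There is no sample size or precision figure to reproduce on this point. The check is schedule arithmetic and a comparison of sections.

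**1. Time to the next scheduled adverse event assessment.**
- After the biopsy (heading of section 6.7.2, with Visit 3 as Day 0): 6 × 7 = 42 days to 8 × 7 = 56 days.
- After the injection (section 6.7.4): 24 to 48 hours, or 1 to 2 days.

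**2. Scheduled adverse event contacts strictly between Visit 2 and Visit 3.** From Table 6-1 and sections 6.7.2 to 6.7.5: none.

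**3. Whether the diary fills the gap.** It starts about 7 days after the biopsy and runs 28 days, so it covers about days 7 to 35. The first week is uncovered, as are the last 42 − 35 = 7 to 56 − 35 = 21 days. Section 6.7.2 describes its content as fecal incontinence data, and it comes back only at Visit 3.

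**4. Scheduled adverse event assessments after the biopsy visit.**
- Injected patient: Visit 3, two calls, and Months 3, 6 and 12, which makes 1 + 2 + 3 = 6.
- Biopsied but never injected: none described. Section 6.8 requires the appropriate case report forms and an exit form with the reason for leaving, but does not mention asking about adverse events at exit.

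Non-injection is foreseeable. The sample may be inadequate (section 6.7.2), or an exclusion at the time of cell delivery may apply (sections 6.4 and 6.7.3).

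**5. Which objective is affected.**
- Biopsy events are study safety data. Table 6-1 collects adverse events from Visit 1 onward, section 2.2 sets no window for the safety objective, and section 6.10 covers all events.
- Their place in the primary objective is unclear. Section 3.5 lists the biopsy among the study's medical or surgical procedures, and section 1.0 states the objective without the post-treatment limit. But section 2.1 counts events within 12 months post-treatment, no definition says that procedure includes the biopsy, and an event before Day 0 falls outside that window as worded.

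**6. Size.** With N patients biopsied, event rate p and probability r that an event is reported at Visit 3, the expected number recorded is N × p × r and the fraction lost is 1 − r. The documents give neither p nor r. Purely as an illustration, assume N = 50, p = 10% and r between 50% and 90%. Then 50 × 0.10 = 5 events occur, and 5 × 0.5 = 2.5 to 5 × 0.9 = 4.5 are recorded, a loss of 10% to 50%. The fraction lost does not depend on p, but it rests wholly on the assumed r. This is not an estimate for this trial.

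**The case against.** The strongest reply is that biopsy events are not ignored.
- Adverse events are recorded on the biopsy day and again at Visit 3.
- Section 6.10 requires every event to be reported once the site knows of it, and monitoring is meant in part to identify events.
- Some patients return within the gap, for a repeat biopsy or for pathogen tests up to seven days after donation.
- Section 5.2 names patient report and the diary among the means of assessing risks such as infection.
- Section 8.0 asks for continued follow-up, if possible, of patients who leave over safety or lack of effectiveness.
- Section 6.8 calls for an attempt to collect safety measures when a patient goes on to another treatment.

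Some relevant text cannot be seen: the interval in section 6.7.3, parts of section 6.7.2, the flow diagram in Appendix A and the separate Procedure Guidelines.

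Much of this stands. A reader might infer that biopsy events are never asked about. For injected patients that is wrong, because Visit 3 asks. A reader might also infer that the primary incidence is biased downward. The documents do not support that either, because an event that section 2.1 does not count cannot bias its estimate. Nor do they show that a biopsy complication would go unmanaged: nothing stops a patient from contacting the site.

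The safeguards still do not amount to routine solicitation. Recording on the biopsy day comes before delayed events. The ten-day rule starts only once the site knows. The return visits in the gap are conditional. Sections 6.8 and 8.0 cover particular reasons for leaving, not a failed biopsy or a cell-delivery exclusion as such.

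**Conclusion.** The point holds as a gap in how biopsy events are collected. Both scheduled calls follow the injection, and no routine adverse event contact is described in the nominal 42 to 56 days from biopsy to Visit 3. Injected patients' short-lived biopsy events depend on recall or spontaneous report. Patients enrolled at biopsy and never injected have no later routine query described.

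The consequence is likely under-recording in the overall safety objective. Extending it to the primary incidence requires two further conditions: that procedure-related includes the biopsy, and that the counting window reaches back before Day 0. The direction follows from the schedule, but the size cannot be computed from the documents.

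The conclusion rests on the visible text and on nominal visit windows, so the true gap may be shorter or longer. This is a low-cost improvement to data collection, not a flaw that invalidates the design.

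**What to change.** - **Section 6.7.2 and Table 6-1:** add one adverse event phone contact after each biopsy. It could use the 24-48 hour interval already used after the injection, or fall at about 1 week, where it would also prompt the start of the diary.
- **Section 6.8:** add an adverse event query before the study exit form is completed for patients who were biopsied but will not be injected.
- **Section 7.2:** report biopsy events separately from injection events, so that a fuller count of biopsy events does not blur the injection results.

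The same amendment could usefully state whether procedure in section 2.1 includes the biopsy and, if so, from what date events count.

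The cost is a protocol amendment and at least 50 × 1 = 50 short calls by existing coordinators. The number rises with repeat biopsies and with patients biopsied but not injected. The reported event rate may come out slightly higher because more events are found.

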6.0 Design of the Clinical Investigation

6.1 Type of Investigation

The proposed investigation will be a prospective, non-randomized, multicenter study to determine the safety and feasibility of AMDC in the treatment of patients with fecal incontinence. The study will treat a total of 50 patients with a dose of 250×10^6 cells.

6.2 Rationale

Despite considerable advances in both the pharmacological and device-related therapeutic strategies, a successful treatment for fecal incontinence that can apply to all patients remains to be developed. Fecal incontinence thus continues to be a debilitating and embarrassing condition for patients world-wide.

AMDC consists of cells derived from skeletal muscle tissue that are expanded *ex vivo*.

[REDACTED] Clinical and non-clinical studies evaluating AMDC have supported these conclusions for the proposed cell therapy.

6.3 Inclusion Criteria

A patient may be enrolled in the study if all of the following inclusion criteria are met:

- Patient has primary symptoms of fecal incontinence, as confirmed by patient medical history and physical examination, including visual inspection, digital rectal examination, anoscopy and/or sigmoidoscopy
- Patient has a Wexner score of ≥ 9 at baseline
- Etiology of FI is related, at least in part, to external anal sphincter dysfunction, as evidenced by external anal sphincter defect (or abnormality) observed on EAUS and/or lower than normal manometric maximum squeeze pressure of $<80\text{mmHg}$
- Patient has failed conservative treatment (e.g. dietary modification, antidiarrheal medications, pelvic floor muscle training, biofeedback) for at least 1 month prior to enrollment

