2.2 Secondary Objectives

The secondary objectives are to study the effect of AMDC treatment for fecal incontinence on:

- Changes from baseline in the frequency and nature of incontinent episodes at 3, 6, and 12 months post-treatment as measured by a patient fecal incontinence diary

- Changes from baseline in Wexner incontinence score [1] (copy provided in Appendix B) at 3, 6, and 12 months post-treatment
- Changes from baseline in Fecal Incontinence Quality of Life Scale (FIQL) [2] (copy provided in Appendix C) scores at 3, 6, and 12 months post-treatment
- Changes from baseline in sphincter function as measured by anorectal manometry at 12 months
- Changes from baseline in sphincter morphology as measured by endoanal ultrasound at 12 months
- Safety as measured by adverse events

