6.6 Sample Size and Dose Allocation

The study will be undertaken at up to five investigative sites. A total of 50 patients will be treated with AMDC. There will be a minimum 1 week delay between the AMDC injection procedures for the first 5 patients.

All patients will receive a cell dose of 250×10^6 ($\pm 20\%$) cells. The Manufacturer will generate the appropriate cell dose and ship it to the Investigator for injection. All AMDC products will be transported in identical vials with the same volume of transport media and reconstituted to the same final volume prior to injection. Vials will be identified by a unique product lot number, which includes the patient identification number, patient initials, and date of collection.

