6.7.1 Visit 1 (Week -16 to -8): Pre-enrollment Screening and Baseline

Informed consent will be obtained and patient medical history will be collected. A physical examination (clinical assessment), including a visual inspection, digital rectal examination, and anoscopy and/or sigmoidoscopy (at physician's discretion), will be performed. Blood samples will be collected to assess for blood-borne pathogens (Hepatitis B, Hepatitis C, syphilis, and HIV) and a risk assessment of HTLV-1 will be performed. If the biopsy procedure takes place more than 30 days after the blood-borne pathogen tests were completed during screening, the blood-borne pathogen tests (i.e. Hepatitis B, Hepatitis C, HIV, and syphilis) and risk assessment of HTLV-1 must be repeated before the biopsy procedure to confirm the patient's continued eligibility for study participation. If applicable, a urine sample will be collected from female patients for pregnancy testing (pregnancy test is not required if the patient has had a previous hysterectomy and/or is post-menopausal). During the visit, the patient will complete the FIQL and Wexner score questionnaires (administered by a member of the research staff). A log of the patient's current medications will be started. Patients will also be instructed not to change (to the greatest degree possible) their medication regimen, and other coping mechanisms, related to their fecal incontinence condition.

In addition, endoanal ultrasound and anorectal manometry tests will be performed prior to the biopsy. Previous exam results may be used for the baseline assessments as long as: 1) they were completed within 6 months prior to enrollment, 2) they collected all required data, and 3) the patient did not undergo any procedures or have any change in condition since the exam that, in the physician's opinion, would be likely to invalidate the previous results.

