All pre-enrollment screening and baseline assessments (e.g. clinical assessment, urine test, ultrasound, manometry, and questionnaires) are recommended to be completed within eight weeks prior to enrollment. Blood tests must be performed within 30 days prior to the biopsy. These blood tests will be repeated prior to any additional biopsies, if more than one biopsy is required. Per manufacturing requirements, patients must be negative for the blood-borne pathogens of Hepatitis B (required tests: Hepatitis B Surface Antigen [HBsAg] and Anti-Hepatitis B Core Total Antibody [Anti-HBc]), Hepatitis C (required test: Hepatitis C Antibody [Anti-HCV]), HIV (required tests: HIV Type 1 and 2 Antibodies [Anti-HIV-1, 2]), syphilis and HTLV-1 (European sites only). At this point the patients will have completed all the necessary screening assessments and, if they meet all entry criteria, may now be enrolled into the study and can be scheduled for the muscle biopsy.

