6.7.3 Visit 3 (Day 0): AMDC Injection Procedure

[REDACTED] after the muscle biopsy, patients will return to the clinic for a brief outpatient procedure. Prior to injection, if appropriate, patients will also have a urine sample collected for pregnancy testing. Patients will also have their temperature measured and be assessed for signs of infection and changes in anorectal condition that may affect the "At Time of Cell Delivery" exclusion criteria. After confirming eligibility, the AMDC product will be prepared and injected into the external anal sphincter in accordance with instructions for use (as described in Section 3.3). Post-injection, injection sites will be inspected for the presence of bleeding or excessive trauma.

The medication log will be updated if necessary and adverse events will be recorded and reported as appropriate. Patients will be reminded not to change (to the greatest degree possible) their medication regimen, and other coping mechanisms, related to their fecal incontinence condition. Patients will be given a 28-day diary to report fecal incontinence data. The diary should be completed during the 28 days leading up to, and returned to the site at, the next scheduled visit (3 Month Follow-up Visit).

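### The single pre-treatment Wexner score is both the entry test (≥ 9) and the baseline for Wexner change, which biases that secondary endpoint toward benefit by an unknown amount

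*Combined protocol and SAP*

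**What the plan says.** - **Entry (6.3):** "Patient has a Wexner score of ≥ 9 at baseline".
- **Endpoint (2.2):** "Changes from baseline in Wexner incontinence score [1] (copy provided in Appendix B) at 3, 6, and 12 months post-treatment".
- **Timing (6.7.1, Visit 1, Week -16 to -8):** "During the visit, the patient will complete the FIQL and Wexner score questionnaires". The same section treats screening and baseline as one set of assessments: "All pre-enrollment screening and baseline assessments (e.g. clinical assessment, urine test, ultrasound, manometry, and questionnaires) are recommended to be completed within eight weeks" before enrollment.
- **Biopsy (6.7.2):** "patients will be given a 28-day diary to report fecal incontinence data and instructions on how to complete the diary". No Wexner score is described.
- **Injection (6.7.3):** "Patients will also have their temperature measured and be assessed for signs of infection and changes in anorectal condition". Again no Wexner score is described.
- **Table 6-1:** the Wexner row has one mark before injection, at Visit 1. The other marks are the 3-, 6- and 12-month visits.
- **Design (6.1, 6.6):** "The proposed investigation will be a prospective, non-randomized, multicenter study"; "A total of 50 patients will be treated with AMDC", all at one dose.
- **Analysis (7.2):** descriptive summaries, which may include means and 95% confidence intervals. There is no test, no success rule and no provision for selection on the baseline score.
- **Limitations (6.9):** small numbers and unknown variables. Regression to the mean is not named.

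**The concern.** A single Wexner reading is the patient's usual level plus occasion-to-occasion noise. Admitting only patients who read 9 or more favours those whose noise was upward on that day. When the same reading is then subtracted from the follow-up score, the upward noise is counted as improvement. This happens whenever the test-retest correlation is below 1, whatever AMDC does.

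With no control arm, nothing in the data separates this shift from a treatment effect. A confidence interval around the mean change does not cover it, and a larger sample would only narrow the interval around a shifted value. Any untreated drift between Visit 1 and injection also enters the change. Its sign is unknown, so it may add to the selection shift or offset it.

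This matters because 7.1 says the sample can show potential efficacy and 6.9 expects the data to support a larger trial. A mean Wexner change that is too favourable could be carried into that trial's planning.

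The point concerns Wexner change only. FIQL has no entry threshold, the diary baseline is collected after the eligibility score, and the primary endpoint is adverse-event incidence.

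**Working it through.** The plan gives no figure to reproduce: 50 patients are stated without an effect size, SD, alpha or power.

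**Inputs from the documents:** threshold ≥ 9 (6.3); n = 50 (6.6, 7.1); one pre-treatment score (6.7.1, Table 6-1).

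**Inputs assumed, because the documents do not give them:**
- The score is an integer, so the cut is 8.5, and higher is worse. The direction is inferred from the entry rule.
- Unselected candidates have mean μ of 10, 11, 12, 13 or 14 and SD σ of 3 or 4.
- Test-retest correlation ρ is 0.6, 0.7, 0.8 or 0.9, the same at every follow-up month.
- There is no drift and no treatment effect. The grid has 5 × 2 × 4 = 40 cells.

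**Formulas (truncated bivariate normal):**
- z = (8.5 − μ)/σ and λ = φ(z)/(1 − Φ(z))
- Shift toward benefit = σ(1 − ρ)λ
- Var(X | X ≥ 8.5) = σ²(1 + zλ − λ²)
- SD of change = √[(1 − ρ)² Var(X | X ≥ 8.5) + σ²(1 − ρ²)], and SE = SD of change/√50
- Chance that a 95% interval lies wholly on the benefit side = Φ(shift/SE − 1.96)

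**One cell in full (μ = 12, σ = 4, ρ = 0.7):**
- z = (8.5 − 12)/4 = −0.875 and λ = 0.336
- Shift = 4 × 0.3 × 0.336 = 0.40 points
- Var(X | X ≥ 8.5) = 9.48
- SD of change = √(0.09 × 9.48 + 16 × 0.51) = 3.00, so SE = 3.00/√50 = 0.425
- Shift/SE = 0.95, and the chance is Φ(0.95 − 1.96) = 15.6%

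**Central cells (μ = 12):**

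| σ | ρ | Shift (points) | Chance interval is wholly on benefit side |
|---|---|---|---|
| 3 | 0.8 | 0.14 | 7.5% |
| 3 | 0.7 | 0.21 | 9.4% |
| 4 | 0.8 | 0.27 | 11.7% |
| 4 | 0.7 | 0.40 | 15.6% |

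**Whole grid:**
- The shift runs from 0.02 points (μ = 14, σ = 3, ρ = 0.9) to 0.92 points (μ = 10, σ = 4, ρ = 0.6), with median 0.21 and quartiles 0.12 and 0.39.
- It is below 0.40 points in 30 of 40 cells and below one standard error in 29 of 40. At μ = 14 it is 0.02 to 0.27.
- The interval chance is 3% to 49%, median 10%, against 2.5% with no shift. This shows scale only, since 7.2 does not commit to an interval for this endpoint.

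**Check of the remedy.** A simulation with rounded scores and independent errors, on the four central cells, gave shifts of 0.14, 0.21, 0.28 and 0.41 points with the Visit 1 baseline. With a separate pre-injection baseline the shift was 0.00 and the interval chance 2.4% to 2.7%.

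If errors are not independent, part of the shift remains. Suppose Visit 1 correlates 0.8 with Visit 3 but 0.7 with follow-up. The residual is then σλ(0.8 − 0.7), against σλ(1 − 0.7) without the change, which is one third: 0.02 to 0.23 points instead of 0.07 to 0.69.

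**The case against.** The other side accepts the facts and argues that they matter little. Wexner is one of several secondary measures in a safety and feasibility study, with no test and no go/no-go rule, and 6.9 already says the study cannot establish effectiveness. The shift may be negligible. That is fair, and it limits the weight of the point. But 6.9 rests on small numbers and unknown variables, whereas this bias has a known direction and does not shrink with sample size.

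A second objection is that medians and cell counts over an assumed grid are not evidence. This also stands: they describe the grid, not the trial. Means of 9–15 and SDs of 3–5, with the same correlations, give a median of 0.29 and a maximum of 1.47 points. Means of 12–15, SDs of 3–4 and correlations of 0.7–0.9 give a median of 0.09 and a maximum of 0.40. The direction is the same in every case, and only the size is open.

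Third, medication and coping mechanisms are to be held constant, and the diary already has a baseline taken after the eligibility score. The first bears on drift and the second gives a cleaner measure alongside, but neither removes the selection shift from Wexner change.

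Last, a Visit 3 baseline would give Wexner and FIQL different reference dates. That is true but minor, because the diary baseline already falls later than the FIQL baseline. FIQL could also pick up some indirect shift if its Visit 1 errors correlate with those of the Wexner score. The documents give no basis for sizing that.

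**Conclusion.** The concern holds. One reading is both the entry test and the baseline, there is no comparator, and neither 7.2 nor 6.9 deals with the resulting bias. The direction rests only on imperfect test-retest correlation and on higher scores being worse.

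The size is not determinable from the documents. Under the 40-cell assumptions it is 0.02 to 0.92 points, and 0.14 to 0.40 in the central cells. It approaches zero if candidates score well above 9 or the score is very stable. The consequence is confined to a descriptive secondary endpoint. The change should be made because it is cheap and the bias is avoidable, but the point does not threaten the primary objective.

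**What to change.** 1. Add a Wexner score before injection at Visit 3, in 6.7.3 and Table 6-1.
2. Define that score in 2.2 and 7.2 as the baseline for Wexner change.
3. In 6.3, tie the unchanged ≥ 9 threshold to screening at Visit 1, and adjust the baseline label for the Wexner score in 6.7.1. Otherwise the words *at baseline* would point to Visit 3. On the assumed grid, 1% to 21% of patients (median 8%, about 4 of 50) would score below 9 at Visit 3 with no treatment effect.
4. Report the Visit 1 to Visit 3 change as the untreated within-patient change, which combines regression to the mean and drift.
5. State in 6.9 that the uncontrolled design leaves placebo response and natural history in the Wexner change.

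The cost is one extra questionnaire at an existing visit, an amendment to 2.2, 6.3, 6.7.1, 6.7.3, 6.9, 7.2 and Table 6-1, and possibly a smaller observed improvement. Some selection shift may remain if errors are correlated, and placebo response and natural history after injection are not removed.

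If Visit 3 cannot be changed, 6.9 should at least say that the entry score is also the baseline and that this favours apparent improvement. That discloses the bias but does not reduce it.
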